### **Tertiary Outcomes.**

Groups will be compared on the collapsed composite of opioid-related side effects in the first 72 hours after surgery using chi-square tests. Groups will be compared on satisfaction with pain management at using a 0-10 point scale at 72 hours, or upon discharge if earlier, using the Kruskal-Wallis test overall and Wilcoxon rank sum test between interventions.

**Economic Analysis.** Finally, if a treatment effect between the 2 local anesthetic TAP blocks is detected, we will conduct a cost-effectiveness analysis estimating the incremental cost-effectiveness ratio (ICER) as the mean difference in costs divided by the mean difference in the primary outcome of time to return of sensation [or an analogous ratio using summaries which best fit the distribution of the data]. Total cost of hospital care and specific care costs will be estimated from data in the electronic medical records database. Data obtained from electronic medical records will include: operation time, surgery type, intraoperative opioid consumption, postoperative opioid consumption in PACU and in ward, breakthrough pain medication requirements, pain scores in PACU and ward, requirement of oxygen in PACU and ward, pruritus, requirement of antihistaminic medications, requirement of naloxone, itching, ambulation time, flatus, ileus, bowel movements (first time documented), constipation, length of stay and any side effects or complications.

**Interim Analyses.** We will use a group sequential design to conduct interim analyses at each 25% of the planned enrollment to assess efficacy and futility of the intervention using a gamma spending function. Specifically, we will maintain the overall alpha level (monitoring efficacy) at 0.05 using gamma parameter of -4 [similar to O'Brien Fleming], and power at 90% (monitoring beta, type II error) using gamma parameter of 0 [more aggressive, similar to Pocock]. Under the alternative hypothesis (assuming a true 50% relative reduction in the primary outcome) the cumulative probability of crossing an efficacy (and futility in parentheses) boundary at the 1st through 4th analyses will be 0.09 (0.025), 0.39 (0.05), 0.75 (0.075) and 0.90 (0.10) as shown in **Figure 1**.

**Figure 1.** Group sequential stopping boundaries as a function of sample size. Pink region represents futility. Lower blue represents efficacy of NAC, upper blue represents harm. Y-axis represents the treatment effect (Z= difference in means divided by standard error).

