## **Amendments**

Amendment 1: 10/1/2021

Summary of Changes:

1. The primary outcome was changed to opioid consumption in the first 24 hours and 24-48 hours after surgery.
2. The secondary outcomes are now abdominal wall sensation with ice and pinprick, pain scores 72 hours after surgery, and opioid consumption 48-72 hours after surgery.
3. Sample Size Considerations was updated to reflect the changes in the study outcomes.

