## **Tertiary**

**Tertiary Aim 1.** To compare the effect of liposomal bupivacaine, conventional bupivacaine, and placebo on a composite of opioid-related postoperative side effects.

**Hypothesis.** Opioid-related side effects over the initial 72 hours or duration of hospitalization after major abdominal surgery are less common when four-quadrant TAP blocks are performed with liposomal bupivacaine than with plain bupivacaine or placebo. Opioid-related side effects will be evaluated as composite of events, and a difference of 20% in incidence will be accepted as clinically important difference.

**Tertiary Aim 2.** To compare the effect of liposomal bupivacaine, conventional bupivacaine, and placebo on satisfaction with their pain treatment after first 72 hours or the duration of hospitalization if shorter.

**Hypothesis.** Patients are more satisfied with pain management over the initial 72 hours or duration of hospitalization after major abdominal surgery when four-quadrant TAP blocks are performed with liposomal bupivacaine than with plain bupivacaine or placebo.

**Tertiary Aim 3.** To assess total and specific costs of hospital care in patients receiving TAP with liposomal bupivacaine vs. those with plain bupivacaine following abdominal surgery.

**Tertiary Aim 4.** To compare the effects of TAP blocks with liposomal bupivacaine, plain bupivacaine and placebo on patients' pain with movement for 72 hours/discharge surgery.

**Hypothesis.** Pain scores with movement over the initial 72 hours or duration of hospitalization after major abdominal surgery are lower when four-quadrant TAP blocks are performed with liposomal bupivacaine than with plain bupivacaine or placebo. Pain will be assessed on a 0-10-point scale (10 points being worst) at 12-hour intervals while patients are elevating their leg. A difference of at least 1.2 points will be considered clinically meaningful.

**Tertiary Aim 5.** To compare the effects of TAP blocks with liposomal bupivacaine, plain bupivacaine and placebo on patients' mobility for 72 hours/discharge surgery.

**Hypothesis.** Total amount of mobilization over the initial 72 hours or duration of hospitalization after major abdominal surgery are higher when four-quadrant TAP blocks are performed with liposomal bupivacaine than with plain bupivacaine or placebo.

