### ***Primary Outcome 1***

Opioid requirements will be measured as the total amount of opioids (converted to morphine sulfate equivalents) used during the first 24 postoperative hours after surgery. Use of PCA and discontinuation will be recorded.

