### ***Primary Outcome 2***

Opioid consumption will be measured as morphine equivalents between 24-48 hours.

To evaluate TAP blocks with liposomal bupivacaine, plain bupivacaine, and placebo on opioid consumption in 24 to 48 hours. Use of PCA and discontinuation will be recorded.

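### The economic analysis rests on an outdated primary outcome and an unnamed trigger, and leaves Tertiary Aim 3 without a planned cost comparison if no effect is detected

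*Combined protocol and SAP*

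**What the plan says.** The Economic Analysis paragraph (section 3.F, under Tertiary Outcomes) states that "if a treatment effect between the 2 local anesthetic TAP blocks is detected, we will conduct a cost-effectiveness analysis". The ratio is "the mean difference in costs divided by the mean difference in the primary outcome of time to return of sensation", followed by a bracket allowing "or an analogous ratio using summaries which best fit the distribution of the data".

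The current outcome sections rank things differently. Primary Outcome 1 in section 3.E reads "Opioid requirements will be measured as the total amount of opioids (converted to morphine sulfate equivalents) used during the first 24 postoperative hours", and Primary Outcome 2 reads "Opioid consumption will be measured as morphine equivalents between 24-48 hours". Time to return of sensation is Secondary Aim 1 in section 2 and Secondary Outcome 1 in section 3.E.

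Tertiary Aim 3 is "To assess total and specific costs of hospital care in patients receiving TAP with liposomal bupivacaine vs. those with plain bupivacaine". It appears in both the Specific Aims and section 2, with no condition and no effectiveness outcome. Tertiary Outcome 3 in section 3.E says that total and specific costs will be estimated from the electronic medical records, also without condition.

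**The concern.** There are three linked problems.

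- **The label contradicts the ranking.** An analyst cannot tell whether the denominator should be the primary outcome (opioid consumption) or time to return of sensation. The plan treats them as the same thing, and they no longer are.
- **The trigger is undefined.** The plan does not say which outcome, which period or which significance level counts as a detected effect. The decision to run the analysis could therefore be taken after the results are known.
- **The aim is unconditional but the analysis is not.** Section 1.E gives cost as a reason why clinicians question liposomal bupivacaine. Section 1.D cites a review that found no advantage in this use and a trial that reported no benefit, so a null result between the active arms is plausible. Cost would then matter most, and no cost comparison is planned for that case.

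A further effect follows from the condition. Estimates kept only when significant tend to be too large, and an inflated denominator can make the ratio look too favourable.

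**Working it through.** **1. Ranking of the denominator.** The amendment list records the change: "The primary outcome was changed to opioid consumption in the first 24 hours and 24-48 hours after surgery". The point does not rest on that list. The Specific Aims, section 2, section 3.E and the Primary Outcomes paragraph of section 3.F all make opioid consumption primary, and all but the last explicitly place sensation among the secondary aims or outcomes. The Economic Analysis paragraph is current analysis text and still calls sensation primary. The paragraph on time to return of sensation, although placed under Secondary Outcomes, likewise ends by referring to the primary outcome. The bracket in the ICER definition allows a different summary statistic to suit the distribution; it does not name a different outcome.

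**2. Candidate triggers.** The documents allow at least three readings of a detected effect between the two active blocks:

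- Opioid consumption at 24-48 h. This is the only primary window with a listed liposomal-versus-plain test, and it is reached only if at least one test in Set #1 is significant.
- Opioid consumption at 0-24 h. Section 2 has a success criterion for one active block over the other, but section 3.F lists no such test.
- Time to return of sensation, tested at 0.05/3 = 0.0167 per comparison.

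**3. What remains if nothing is detected.** Costs are estimated in any case. The only between-arm cost quantity in the plan is the ICER numerator, and that belongs to the conditional analysis. No other estimator, interval or test for the cost difference is given.

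**4. Effect of conditioning on significance.** The plan states no ICER, cost figure or power for time to return of sensation, so there is no figure to reproduce. This is an illustration under assumptions: the standardised effect estimate is Z ~ N(δ, 1), with δ = c + z(power); the analysis runs only if Z > c; and the cost difference is independent of Z.

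Inflation of the denominator when the trigger is the denominator itself is 1 + φ(c − δ) / (power × δ). With c = 1.96 (two-sided 5%):

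- 90% power: δ = 1.96 + 1.282 = 3.242; 1 + 0.1755 / (0.90 × 3.242) = 1.06
- 80% power: δ = 1.96 + 0.842 = 2.802; 1 + 0.2800 / (0.80 × 2.802) = 1.12
- 50% power: δ = 1.96; 1 + 0.3989 / (0.50 × 1.96) = 1.41

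The mean ICER relative to its true value is δ × E[1/Z | Z > c], taken from two million simulated draws. The last column takes a trigger correlated 0.3 with the denominator, with equal standardised effects, for which the inflation is 1 + 0.3 × (inflation − 1).

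| Power | Denominator inflation, 5% | Mean ICER / true, 5% | Denominator inflation, 0.0167 | Mean ICER / true, 0.0167 | Denominator inflation, correlation 0.3, 5% |
|---|---|---|---|---|---|
| 90% | 1.06 | 1.00 | 1.05 | 1.00 | 1.02 |
| 80% | 1.12 | 0.94 | 1.11 | 0.94 | 1.04 |
| 50% | 1.41 | 0.74 | 1.33 | 0.77 | 1.12 |

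With zero correlation the inflation is 1.00 at every power. At 20% power and a 5% trigger on the denominator itself, it is 2.25 and the mean ICER is 0.46 of its true value.

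**The case against.** The strongest reply is that this is a tertiary, two-arm aim that touches neither the primary conclusions nor the type I error, and that much of the criticism could be pushed too far. Four stronger inferences are tempting, and the documents support none of them.

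- **That the ICER is biased.** This needs the trigger to be significance on the denominator, or on something correlated with it, and the plan names no trigger. At 90% power, the level section 3.G plans for opioid consumption, the mean ICER is essentially unbiased even when the trigger is the denominator. Inverting the mean inflation would suggest understatement of 6%, 11% and 29% (1/1.06 = 0.94, 1/1.125 = 0.89, 1/1.407 = 0.71). That is the reciprocal of an average, not the average of the reciprocal; the latter gives about 0%, 6% and 26%. The direction also assumes that liposomal bupivacaine costs more overall. The documents give no costs, and length of stay is among the recorded items, so a saving is possible.
- **That Tertiary Aim 3 goes unanswered.** Costs are estimated unconditionally, and the ICER numerator is the required cost difference. What is missing is an unconditional comparison.
- **That sensation is the wrong denominator.** A secondary outcome may serve, and block duration is a stated aim. The error is the label and the unstated choice.
- **That 24-48 h opioid use must replace it.** Nothing in the documents prescribes an outcome for the economic analysis.

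The reply therefore limits the bias argument and the choice of remedy. It does not remove the label conflict, the unnamed trigger or the missing unconditional comparison, none of which depends on a calculation.

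**Conclusion.** The point holds on the text. The ICER is tied to an outcome described as primary that is now secondary, and its trigger names no outcome, period or significance level. If no effect is detected between the active blocks, the plan contains no between-arm cost comparison for an aim stated without condition.

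Selection on significance is a possible further distortion, not an established bias. For powers of 50% to 90% and a 5% trigger on the denominator itself, the mean ICER lies between about 0.74 and 1.00 of its true value; it could be further off at lower power. There is no inflation of the denominator if the trigger is uncorrelated with it. These figures assume normal theory and a cost difference independent of the effect; the power values are assumptions, since the plan gives none for sensation. The consequence is confined to the economic aim.

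**What to change.** Amend the Economic Analysis paragraph as follows.

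1. Remove the condition that an effect must first be detected.
2. Always compare mean total and specific costs between the two active arms, with a confidence interval (for example, bootstrap).
3. Report incremental cost and incremental effect jointly, as the ICER with a cost-effectiveness plane, whatever the significance of either.
4. Name the effectiveness outcome under its current rank. One option is the arithmetic mean difference in morphine equivalents (mg) at 24-48 h, the only primary window with a listed liposomal-versus-plain test. This must be defined separately, because the primary analysis gives only ratios of geometric means. If time to return of sensation is kept, call it secondary and use a mean restricted to the 72 h assessment limit, since testing stops there and the planned analysis reports medians.
5. Correct the same leftover reference to the primary outcome in the paragraph on time to return of sensation.

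The cost is SAP wording and a small amount of extra analysis. The cost data are already to be collected.

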#### ***Criterion for success of each intervention in each period.***

0-24 hours: for each of bupivacaine and exparel, success will be concluded if found to be superior over placebo (i.e., less opioid consumption). As well, exparel or bupivacaine will be concluded better than the other if found superior on opioid consumption.

24-48 hours: exparel will be concluded successful if found better than both placebo and bupivacaine in the 24-48 hours opioid consumption.

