## **F. Data Analysis**

Randomized groups will be compared for baseline balance using standard descriptive statistics and the standardized difference (difference in means or proportions divided by the pooled standard deviation).

**Primary Outcomes.** *Opioid consumption.* The following tests for superiority on opioid consumption will be conducted (see type I error control below): 1) 0-24 hours post-surgery: compare each of exparel and plain bupivacaine to placebo; and 2) 24-48 hours post-surgery: compare exparel to each of plain bupivacaine and placebo. Groups will be compared using linear regression on log-transformed morphine equivalents, with results reported as ratio of geometric means between each pair of interventions.

**Type I error control across Primary outcomes 1 and 2.** We will use a parallel gatekeeping procedure to control the type I error at 5% across the 2 primary outcomes. The 2 comparisons for the 0-24 hour period will constitute Set #1, and the 2 comparisons for the 24-48 hour period will constitute Set #2. Within each set we will use the Holm-Bonferroni (HB) multiple comparison procedure among the two comparisons. If either test in the first Set is significant (HB: significance criterion of 0.025 for smaller P-value and 0.05 for the larger), analysis will continue to Set #2. Otherwise, Set #2 will not be analyzed. If analysis proceeds to Set #2, the overall alpha for Set #2 will be  $0.05 \times$  proportion of significant tests in Set #1 (i.e., Set #2 alpha = either  $0.05 \times 1$  or  $0.05 \times .5 = 0.025$ ).

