## G. Sample Size Considerations

We plan the study to have 90% power at the overall 0.05 significance level to be able to detect a relative improvement of 40% or more in mean opioid consumption(i.e., ratio of geometric means of 0.60) between any of the 3 interventions, assessing separately for 0-24 hours (primary outcome #1) and 24-48 hours (primary outcome #2) postoperatively. Assuming a coefficient of variation (CV = SD/mean) for opioid consumption of 0.85 [since the outcome is expected to be log-normal], the required sample size to will be 67 per group or 201 total. After adjusting for the interim analyses the maximum sample size will be 79 per group or a total of 237. Alternatively, for example, a total (maximum) sample size of 722 would be required to detect a more modest 25% reduction in the mean.

Internal pilot assessment of variability. At the second interim analysis, we will conduct an internal pilot study to assess the observed variability in the primary outcome and the related coefficient of variation (CV). If the CV is larger than planned in the protocol, we will resize the study accordingly, keeping everything else the same. For example, if the observed CV is 1.0 (instead of 0.85), the new maximum sample size would be a total of 298 patients to detect the same 40% relative reduction in the outcomes. The internal pilot assessment will not affect the type I error of the study nor alter the effect size of interest.

Adaptive design option. At the 3rd interim analysis we may consider an adaptive design in which the study is repowered for a smaller but still clinically important treatment effect. Specifically, if the conditional power at the 3rd look is between 30% and 75%, the DSMB (or Executive Committee) we will consider resizing the study to have 90% power to detect a relative reduction as small as 20% (i.e., a ratio of geometric means of 0.80). 

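### The interim plan gives one stopping boundary for four gated primary comparisons and names no trigger, so a 0-24 h win over placebo could end enrolment before the 24-48 h liposomal-versus-plain test is adequately powered

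*Combined protocol and SAP*

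**What the plan says.** **Primary tests (section 3.F, Primary Outcomes and Type I error control).** Set #1 compares liposomal and plain bupivacaine each with placebo at 0-24 h. Set #2 compares liposomal with plain and with placebo at 24-48 h. Holm applies within each set (0.025, then 0.05). Set #2 opens "If either test in the first Set is significant", with alpha 0.05 if both Set #1 tests succeed and 0.025 if one does. These are single-analysis criteria and refer to no interim look.

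**Success (section 2, Criterion for success).** At 24-48 h, "exparel will be concluded successful if found better than both placebo and bupivacaine in the 24-48 hours opioid consumption".

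**Interim looks (section 3.F, Interim Analyses).** The design is "to conduct interim analyses at each 25% of the planned enrollment to assess efficacy and futility of the intervention". Overall alpha is 0.05 with gamma -4, and beta is 0.10 with gamma 0. One row of cumulative efficacy crossing probabilities is given (0.09, 0.39, 0.75, 0.90). It is labelled as assuming a 50% reduction in a single primary outcome.

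**Sample size (section 3.G).** "We plan the study to have 90% power at the overall 0.05 significance level" for a 40% reduction (ratio of geometric means 0.60) "between any of the 3 interventions, assessing separately for 0-24 hours (primary outcome #1) and 24-48 hours (primary outcome #2) postoperatively". This gives 67 per group, or at most 79 per group after allowing for the looks.

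**The concern.** The interim section does not say:

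- which of the four comparisons is monitored;
- whether one crossing or several are needed to stop;
- how the spent alpha relates to the Holm and gatekeeping levels;
- whether enrolment continues for Set #2 once Set #1 has crossed.

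A monitoring board could not apply the rule without inventing these parts.

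The gap matters because Set #1 is likely to cross first. Background section C already reports that plain bupivacaine blocks beat placebo for up to 24 hours. The Specific Aims and the rationale (section 1.E) describe liposomal versus plain as the unsettled question. A stop on Set #1 would leave the second primary outcome with fewer patients than the 90% power statement assumes.

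**Working it through.** **Inputs.** Ratio 0.60, CV 0.85, 90% power, 67 and 79 per group (section 3.G). Four equal looks, gamma -4 for alpha, gamma 0 for beta (section 3.F). Log difference = ln(1/0.60) = 0.511. Log SD = sqrt(ln(1 + 0.85²)) = 0.737.

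**1. The plan's sample size.** n per group = 2 × (0.737/0.511)² × (z(alpha/2) + 1.282)² = 4.17 × (z(alpha/2) + 1.282)².
- Alpha 0.05: 4.17 × (1.960 + 1.282)² ≈ 44.
- Alpha 0.05/6 (three pairs × two periods): 4.17 × (2.638 + 1.282)² ≈ 65, or 66 with the t distribution. The plan states 67.
- Group-sequential inflation at 0.05/6 is 1.162, and 67 × 1.162 ≈ 78. The plan states 79.

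Of the natural choices, only about 0.05/6 reproduces the sizing, whereas the monitoring text names a single 0.05.

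**2. The plan's crossing probabilities.** At alpha 0.05 the boundaries are z = 3.155, 2.818, 2.439 and 2.014. For a design with 90% power, the crossing probabilities are 0.083, 0.383, 0.735 and 0.90, within 2 points of the stated row. At 0.05/6 they are 0.063, 0.360, 0.731 and 0.90. The row fits 0.05 slightly better but does not settle which alpha was used. A 50% reduction would need only about 4.17 × (0.511/0.693)² × 15.4 ≈ 35 per group at 0.05/6. A row ending at 0.90 with 79 per group therefore belongs to the 40% effect.

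**3. Power of one 24-48 h comparison at each look.** Drift = 0.511/(0.737 × sqrt(2/n)). Boundary power = Phi(drift - z).

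| Look | n per group | Drift | Power at alpha 0.025 / 0.05 | Power on the 0.05 boundary |
|---|---|---|---|---|
| 1 | 20 | 2.19 | 0.48 / 0.59 | 0.17 |
| 2 | 40 | 3.10 | 0.80 / 0.87 | 0.61 |
| 3 | 59 | 3.76 | 0.94 / 0.96 | 0.91 |
| 4 | 79 | 4.35 | 0.98 / 0.99 | 0.99 |

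The shortfall comes from stops at looks 1 and 2. On the stricter 0.05/6 boundary (z = 3.044 at look 3), a look 3 stop also falls short: Phi(3.76 - 3.04) ≈ 0.76.

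**4. Joint simulation.** 40,000 runs, three arms, two periods, at most 79 per group, no futility stop, correlation 0.5. Both active arms have a ratio of 0.60 to placebo at 0-24 h. At 24-48 h, liposomal has 0.60 to plain, and plain equals placebo.

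| Boundary alpha | Stopped by looks 1, 2, 3 if either 0-24 h test triggers | 24-48 h liposomal vs plain crossed by that stop | Same, if both 0-24 h tests must cross | Same, with no 0-24 h stop |
|---|---|---|---|---|
| 0.05 | 0.27, 0.77, 0.97 | 0.57 | 0.76 | 0.99 |
| 0.05/6 | 0.13, 0.56, 0.89 | 0.54-0.55 | about 0.74 | 0.95 |

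With correlations from 0 to 0.8, the either-trigger figures stay within 0.54-0.58. If Set #2 is instead tested at unadjusted Holm levels at the stop, power is 0.75-0.83 (p<0.025) or 0.81-0.88 (p<0.05). With the 0.05 boundary and the either trigger, beating both comparators at 24-48 h is reached in 46% of runs, against 98% without the stop.

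**5. Type I error.** Two tests share the placebo arm, each monitored two-sided at 0.05. The chance that at least one crosses under the null lies between 0.05 and 1 - 0.95² = 0.0975. Simulation gives about 0.09, counting crossings in either direction.

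**The case against.** A reader might infer that the plan stops on a 0-24 h win, or that one futile comparison ends the rest. The text says neither. The conjunctive success criterion in section 2 (Primary Aim 2) could even be read as requiring the 24-48 h result before any stop, although the interim section makes no such link. The defect is an undefined trigger, not a stated rule.

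A per-comparison boundary is not excluded either, since the sizing reproduces near 0.05/6. The interim text may be carry-over: its figure caption names a drug that is not in this trial, and the economic analysis still calls return of sensation the primary outcome. That may explain the gap, but it does not supply a rule.

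The loss can also be put more mildly. Suppose one comparison triggers the stop, with the plan's own increments (0.09, 0.30, 0.36, remainder 0.25) and independent tests. Power at alpha 0.025 is then 0.09×0.48 + 0.30×0.80 + 0.36×0.94 + 0.25×0.98 ≈ 0.87, and about 0.91 at 0.05. That stands for a single trigger at unadjusted levels. On the 0.05 boundary the same weights give 0.09×0.17 + 0.30×0.61 + 0.36×0.91 + 0.25×0.99 ≈ 0.77. With two possible triggers the loss is larger (step 4). It would be wrong to present the look 1 power alone as the trial's power, or the stated 0.39 and 0.75 as the chance of a premature stop: those are single-comparison figures labelled with a different effect size.

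**Conclusion.** The concern holds as a gap in the specification with a material consequence. The plan does not connect its single boundary to its four gated tests, and it does not protect enrolment for Set #2. If a 0-24 h crossing is allowed to stop the trial, 24-48 h liposomal versus plain has crossed in about 54-57% of runs (either trigger) or 74-76% (both required). That compares with 95-99% without the stop and the 90% stated. At unadjusted Holm levels the either-trigger figure is 75-88%. A stop at look 3 leaves over 90% at Holm levels or on the 0.05 boundary. If the single 0.05 boundary is used for both Set #1 tests, family-wise error is about 9%; this does not apply if the Holm levels are carried into the boundaries, which the plan does not say.

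The assumptions that are mine are plain equal to placebo at 24-48 h, the between-period correlation, equal log SD in all arms and periods, and no dropout. If the true 24-48 h liposomal-to-plain ratio were 0.75 (with plain 0.80 of placebo), only 13-19% would have crossed by an either-trigger stop.

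**What to change.** In section 3.F and the monitoring board's charter:

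1. Give each of the four comparisons its own boundary, spending its Holm/gatekeeping alpha by the gamma -4 function, in place of one shared 0.05.
2. State that a Set #1 crossing is recorded but does not end enrolment. Efficacy stopping requires the gate to be open and both 24-48 h liposomal comparisons (versus plain and versus placebo) to have crossed, at the same or different looks.
3. State that futility of a single 0-24 h comparison does not stop the trial. Tie any futility stop to the criterion that liposomal must beat both comparators at 24-48 h.
4. Restate the crossing probabilities for the 40% effect used in section 3.G.

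The cost is wording and fewer early stops. The maximum stays at 79 per group: the smallest gatekeeping level is 0.025/2 = 0.0125, which is less strict than the 0.05/6 at which 79 per group still gives about 0.95 for liposomal versus plain.

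### The gatekeeping rule for the two primary outcomes can let familywise error reach about 6–7% instead of the promised 5%; separately, the interim crossing probabilities carry a 50% label but belong to the 40% design

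*Combined protocol and SAP*

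**What the plan says.** **Testing rule (F. Data Analysis, type I error paragraph).** The plan commits to a "parallel gatekeeping procedure to control the type I error at 5% across the 2 primary outcomes". Set #1 holds the two 0–24 h comparisons, exparel and plain bupivacaine each against placebo. Set #2 holds the two 24–48 h comparisons, exparel against plain bupivacaine and against placebo. Holm is applied within each set, so in Set #1 the criteria are 0.025 and then 0.05. One Set #1 success is enough to open Set #2. The alpha for Set #2 is 0.05 times the share of Set #1 tests that succeeded: 0.025 after one, 0.05 after two. This paragraph does not mention interim looks.

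**Success criteria (Study Objectives).** At 0–24 h each drug is judged on its own against placebo. At 24–48 h exparel must beat both comparators.

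**Interim Analyses.** Looks are planned at each quarter of enrolment: "we will maintain the overall alpha level (monitoring efficacy) at 0.05 using gamma parameter of -4", with futility spending at gamma 0 and 90% power. The text continues "Under the alternative hypothesis (assuming a true 50% relative reduction in the primary outcome) the cumulative probability of crossing an efficacy" boundary and gives 0.09, 0.39, 0.75 and 0.90, with futility 0.025, 0.05, 0.075 and 0.10.

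**G. Sample Size Considerations.** The target is 90% power to "detect a relative improvement of 40% or more in mean opioid" consumption, with a CV of 0.85: "the required sample size to will be 67 per group or 201 total". Then: "After adjusting for the interim analyses the maximum sample size will be 79 per group or a total of 237". For comparison, "a total (maximum) sample size of 722 would be required to detect a more modest 25% reduction in the mean". The internal-pilot example (298 patients if the CV is 1.0) is sized "to detect the same 40% relative reduction in the outcomes".

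**The concern.** Parallel gatekeeping can pass alpha forward only if the first set has not already used it. Full Holm keeps nothing back. Once one Set #1 test succeeds, the other is tested at the whole 0.05. If that second test fails, the plan still hands 0.025 to Set #2. The confirmatory claim for both primary outcomes rests on this paragraph, and the 5% guarantee has to hold whichever hypotheses happen to be true. One-drug success is also a result that the success criteria explicitly allow for.

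The 50% label matters less. Anyone using the Interim Analyses text to judge how often the trial would stop early is given figures for the wrong effect size.

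**Working it through.** **1. Familywise error of the rule as written**

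Inputs: criteria 0.025 and 0.05 in Set #1; carry-over 0.05 × 1/2 = 0.025 after one success (F. Data Analysis). The documents give no correlation between the two periods, so 0 to 0.9 is assumed.

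Suppose one drug works at 0–24 h and is always detected.
- The other, null Set #1 test is judged at 0.05, so a false rejection there has probability 0.05.
- Otherwise (probability 0.95) Set #2 opens at 0.025.
- If one 24–48 h null is true and the other Set #2 effect is detected, Holm tests that null at 0.025. With independent tests the error is 0.05 + 0.95 × 0.025 = 0.0738.
- If both 24–48 h nulls are true, each is first judged at 0.0125. With independent tests the error is 0.05 + 0.95 × [1 − (1 − 0.0125)²] = 0.05 + 0.95 × 0.0248 = 0.0736.

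The tests are in fact correlated through shared arms and repeated use of the same patients. Simulation of the four two-sided tests (three arms, two periods, single analysis, 2,000,000 replicates) gives:

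| True state | Correlation 0 / 0.5 / 0.9 |
|---|---|
| Only exparel works at 0–24 h, always detected; both 24–48 h nulls true | 0.072 / 0.071 / 0.068 |
| Only plain bupivacaine works at 0–24 h, always detected; both 24–48 h nulls true | 0.072 / 0.069 / 0.061 |
| One drug works at 0–24 h, always detected; only exparel vs plain bupivacaine null at 24–48 h | 0.074 / 0.073 / 0.070 |
| Exparel effect 40% at 79 per group; both 24–48 h nulls true | 0.071 / 0.069 / 0.063 |
| Neither drug works in either period | 0.046 |
| Both drugs work at 0–24 h; both 24–48 h nulls true | 0.046–0.047 |
| Only exparel works at 0–24 h and it beats both comparators at 24–48 h | 0.050 |

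The interim looks do not cure this. With each criterion spent over four looks and every test followed to the last look, the first row becomes 0.069–0.072.

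**2. The remedy under the same check**

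- Set #1 at 0.025 each, same carry-over: 0.025 + 0.975 × 0.025 = 0.0494 for independent tests. Simulated values do not exceed about 0.049.
- Truncated Holm (larger Set #1 p-value at 0.0375, carry-over 0.05 − 0.0375 = 0.0125 after one success): 0.0375 + 0.9625 × 0.0125 = 0.0495.

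**3. The 50% label**

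Inputs: CV 0.85, 67 and 79 per group (G. Sample Size Considerations). Log-scale SD = √ln(1 + 0.85²) = 0.737. Per-group size n = 2 × 0.737² × (z for alpha + z for power)² / (ln ratio)².
- For a 40% reduction, ln 0.60 = −0.511. This gives 44 per group at two-sided 0.05 and 64–66 at 0.05/6, depending on the small-sample correction. The latter is close to the stated 67. That 0.05/6 was used is an inference; the plan does not state the sizing alpha.
- For a 50% reduction, ln 0.50 = −0.693. This gives only 24–35 per group over the same alphas, so 67 is not a 50% design.
- The 722 example gives 722/237 = 3.05. Scaling from 40% predicts (ln 0.60/ln 0.75)² = 3.15; scaling from 50% predicts 5.81.
- The 298 example gives 298/237 = 1.26, against a variance ratio of 1.27. That ratio is the same for any effect size, but the text there names 40%.

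The printed futility figures are 0.10 spent in equal quarters, which is what gamma 0 means at the design alternative. A 90%-power design at two-sided 0.05 with non-binding futility gives efficacy crossing of 0.083/0.383/0.733/0.90, within two points of the printed values. Its inflation factor is 1.19, against 79/67 = 1.179.

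At 79 per group the drift is 0.511/(0.737 × √(2/79)) = 4.354 for 40% and 5.908 for 50%. A true 50% reduction would cross for efficacy with probability about 0.80–0.91 by the second look and about 0.996–0.999 by the fourth, with futility stopping under 0.5%. These ranges cover boundary alphas from 0.05/6 to 0.05. A 40% reduction gives 0.07/0.39/0.77/0.92 with boundaries at 0.05/6 and 0.16/0.61/0.91/0.97 at 0.05.

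**The case against.** **The triggering state may be unlikely.** The exparel mixture contains plain bupivacaine, the Background reports benefit from plain bupivacaine for about 24 hours, and Primary Aim 1 expects both drugs to work. In that state error stays below 5%. It is also 0.050 if exparel beats both comparators at 24–48 h, which is the hypothesis of Primary Aim 2. This stands as a limit on how often the excess would arise. It does not rescue a 5% promise made without conditions.

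**About 7% needs near-certain detection.** With 90% power for the effective drug and both 24–48 h nulls true, the error is 0.053–0.065. This is correct, and still above 5%.

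**The success criterion is stricter than the tests.** A lone Set #2 rejection is not a 24–48 h success for exparel. Counting false Set #1 rejections plus false 24–48 h success claims, the case with both 24–48 h nulls true gives about 0.053. The figure returns to 0.071–0.074 where plain bupivacaine fails at 0–24 h but equals exparel and beats placebo at 24–48 h, which fits poorly with the Background. This reduces the practical consequence, but the 5% claim in F. Data Analysis covers the tests themselves.

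**Direction.** The figures count rejections in both directions. False rejections in favour of superiority alone total about 0.031–0.040. If 5% means two-sided error, which is how the criteria read, the excess remains.

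**Stronger readings of the label.** A reader might infer from the 50% label that the trial is mis-sized or its boundaries are wrong. The documents do not support that: 67, 79 and 722 are all consistent with 40%, and the 298 example names 40%. A reader might also treat an apparent sizing alpha near 0.05/6 as a fault, but sizing more conservatively than testing is not an error.

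**Conclusion.** The type I error paragraph is wrong as written. Under exactly one detected drug effect at 0–24 h and at least one true null at 24–48 h, two-sided familywise error is about 0.061–0.074, with 0.074 as the ceiling over the assumed correlations. With a 40% exparel effect at 79 per group and both 24–48 h nulls true it is about 0.063–0.071. The wider reading, that error is near 7% whenever one drug works or in the trial generally, is not supported, because the three states named above keep it at or below about 0.05.

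The 50% in Interim Analyses is a labelling error of minor weight. It misstates early-stopping behaviour and changes nothing else.

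Three further points are drafting clarifications, not errors in their own right: how the single 0.05 spending function relates to the four gatekept tests, whether futility is binding, and a Figure 1 legend that names a treatment not in this trial. The 79/67 inflation fits non-binding futility, but that is an inference.

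**What to change.** **F. Data Analysis, type I error paragraph.** In Set #1, change the criterion for the larger p-value from 0.05 to 0.025 and keep the proportion rule for Set #2. Alternatively, use truncated Holm: 0.0375 for the larger Set #1 p-value, with Set #2 alpha 0.0125 after one success and 0.05 after two.

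Cost: no extra patients. If both drugs truly reduce consumption by 40% at 79 per group, the chance that both Set #1 tests succeed falls from 98.2% to 96.5% with the first option or 97.6% with the second (four looks, no futility stops).

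**F. Data Analysis, Interim Analyses.** Change 50% to 40%, and check the crossing probabilities against the alpha actually used for the boundaries, since at 79 per group they depend on it. Cost: one word and a rerun of the boundary software.

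**While editing.** State that each criterion is that comparison's total two-sided alpha, spent over the four looks, if that is the intention. State which comparison's crossing stops enrolment, whether futility is binding, and which alpha lies behind 67 and 79 per group. Correct the Figure 1 legend.
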